A database will be created to accumulate all of the clinical information generated during this study. No identifiers, apart from name and DOB, will be collected. All data will be stored in databases kept in a study folder created at PI's computer (password-protected). Main database will include aforementioned identifiers, however, each subject will have a unique study ID assigned, and once an analytic table is created, all PHI will be removed from the table (after approval by the PI). Only this de-identified dataset with unique study ID's will be used for statistical analyses. Therefore, the risk to the privacy of the individuals will be minimized.

The access to the research folder and its contents will be restricted to the research staffs listed in this submission form. The PHI will be kept in the main database until completion of the study. The main database containing PHI will be kept in the study folder and will be never transferred out without de-identification of the data. No hard copy research data will be generated in this project.

In order to quantify the muscle mass at the level of L3, electronic copies of abdomen CT-scans with no identifiers will be shared with [name] from the University of Alberta, in Canada. After proper quantification an analytic table including unique study ID's will be sent back to UAMS for integration into the main database.

Risks and Benefits

CRET is a safe procedure and the risk for having a complication, such as an acute coronary syndrome is mostly related to underlying chronic disease. The risk of death varies as well, from 1 death in 20,000 - 70,000 tests, depending mostly on the presence of underlying heart disease. In cohorts including healthy subjects, no deaths or major complications have been observed. Since LT candidates have to undergo a thorough cardiopulmonary evaluation and patients with any moderate to severe cardiopulmonary condition are not considered transplant candidates the risks for any major complication or death in this study should equal zero. Moreover, the personnel taking care of CRET constantly monitors physiologic responses to exercise (including electrocardiogram monitoring), and are trained to stop the test whenever there are signs for an impending complications, and can immediately and effectively perform cardiac resuscitation.

Unlike CRET, in the 6MWT each patient determines the intensity of their exercise according to symptoms and cardiorespiratory fitness. The 6MWT is thus considered a very safe procedure, and it has been performed (without electrocardiogram monitoring) in thousands of older persons and thousands of patients with heart failure or cardiomyopathy without serious adverse events. Although patients with cardiopulmonary disease may be at increased risk for arrhythmias or cardiovascular collapse during testing, it is very unlikely for a complication to be witnessed given the selection criteria followed during LT evaluation (as above).

The risks associated with placement of an IV catheter and blood collection from a vein are minor bleeding, bruising, infection (a small risk any time the skin is broken), or needing more than one attempt to locate veins.

Both CT and DXA scans are associated with exposure to small amounts of ionizing radiation. The abdominal CT-scan will be restricted to a simple phase (non-contrasted) in order to limit radiation exposure, and thus it should not exceed 10 mSv. Since the initial CT-scan is performed as part

Title: A physical activity program in end-stage liver disease
PI: [name]

of the LT evaluation (standard of care), the study will derive in radiation exposure of approximately 20 mSv. This is a very low radiation exposure that might be associated with a low additional increase in lifetime risk for cancer (1 in 1000 to 10,000). In the case of DXA, exposure per whole-body scan is similar to daily background natural radiation exposure (0.01 mSv).

The electrical current used in bioelectrical impedance is very small and thus unlikely to stimulate electrically excitable tissues, particularly cardiac and nervous tissues. Moreover, there are no reports of untoward effects among thousands of individuals in whom bioelectrical impedance analysis has been performed. Actually, the currents employed are very small and below the threshold of perception.

No complication is properly expected from the exercise program since each patient will tailor her/his own intensity of exercise according to individual fitness and symptoms that might occur while exercising (i.e. fatigue, or shortness of breath). Although there is a theoretical increased risk for variceal bleeding and HE, these complications have not been observed in prior studies. Moreover, the CRET and ammonia and lactic acid determinations (obtained with ammonia/lactate thresholds) would provide the investigator with some sense of risk for complications during intense exercise and could adequately advise patients at a higher risk for complications to avoid moderate to intense exercise.

The database containing PHI will remain within UAMS firewall and only used for specific research purposes in this project. Aggregated data will be analyzed and published, but specific data elements will not be made available. Further, subjects will not forfeit any rights by participating - their health care and eligibility for health benefits will not be affected in any way. Although a breach in confidentiality is always a risk when collecting personal information from patients, we believe this is small given the system that has been developed to obtain and handle data.

[figure not shown]
All participants might benefit from study by increasing their physical fitness and dietary habits during and after the study, and they will be able to keep their Fitbit to continue monitoring physical activity.

Ethics

[figure not shown]
This study will be conducted according to US and international standards of Good Clinical Practice (FDA regulations) for all studies. Applicable government regulations, University of Arkansas for Medical Sciences research policies and procedures will also be followed. This protocol and any amendments will be submitted and approved by the University of Arkansas for Medical Sciences Institutional Review Board (IRB) to conduct the study. All subjects for this study will be provided a consent form describing this study and providing sufficient information in language suitable for subjects to make an informed decision about their participation in this study. The formal consent of a subject, using the IRB-approved consent form, will be obtained before that subject is submitted to any study procedure. This consent form must be signed by the subject or legally acceptable surrogate, and the investigator-designated research professional obtaining the consent.

Figure 1. Plots showing $\dot{V}O_{2\text{max}}$, anaerobic, and lactate/ammonia thresholds.

1a

1b

1c

[figure not shown]

Figure 2. Relationship between SONIC and West Haven (WH) criteria.

[figure not shown]

Table 1. West Haven criteria for diagnosis and classification of overt hepatic encephalopathy.

West Haven	Features
Grade 0	No abnormalities detected
Grade 1	Trivial lack of awareness Euphoria or anxiety Shortened attention span Impairment of addition or subtraction
Grade 2	Lethargy or apathy Disorientation for time Obvious personality change Inappropriate behavior
Grade 3	Somnolence to semi-stupor Response to stimuli Confused Gross disorientation Bizarre behavior
Grade 4	Coma, unable to test mental state

BIBLIOGRAPHY

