End-stage liver disease (ESLD) is the final consequence of cirrhosis and portal hypertension, causing great morbidity and mortality, and necessitating liver transplantation (LT) to preserve life.(1) Physical fitness is defined as the ability to carry out daily tasks with vigor and alertness, without undue fatigue.(2) Compared to healthy peers, patients with ESLD have a poor physical fitness, and deterioration progresses along with liver failure. Patients with chronic liver disease (with or without cirrhosis) have low to limited activity, with daily pedometer counts between 5000-7000 steps per day, what is way below a minimum recommended of 10,000 daily steps, for a "somewhat active" individual.(3-5) There are several reasons for patients with cirrhosis having low to limited physical activity. Some of the most common contributing factors include chronic fatigue, muscle wasting, obesity, intentional inactivity (either physician-prescribed or self-imposed due to disease misconceptions), poor motor and visuospatial coordination in relation to hepatic encephalopathy (HE), covert HE-associated fear of falling, ascites and fluid overload limiting mobility, and concomitant cardiopulmonary diseases (hepatopulmonary syndrome, portopulmonary hypertension, cirrhotic cardiomyopathy).(6, 7)

Severe skeletal muscle loss or sarcopenia is one of the end results of a limited physical fitness, and it is also a major feature of malnutrition. Notably, sarcopenia and HE are closely related and they can perpetuate or aggravate each other. Since skeletal muscle represents the major organ participating in extrahepatic ammonia metabolism, it is not surprising to find that patients with sarcopenia and malnutrition have a higher risk for HE.(8, 9) On the other hand, HE negatively impacts muscle mass by affecting motor coordination and physical activity, and experimental data have also shown that hyperammonemia has a detrimental impact on skeletal muscle by favoring cell autophagy.(10)

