 - It is expected to find improved anthropometrics, decreased fatty mass, and increased fat-free mass in the active arm, when compared to the control arm.
- The changes in quality of life at the end of the study for each group.
 - It is expected to find improvements in quality of life in the active arm, when compared to the control arm.
- Safety of the physical training program, by systematically documenting episodes of variceal bleeding, and hepatic encephalopathy.
 - No increased risk for complications such as GI bleeding and encephalopathy is expected for the active arm with current research design.
- The changes in the metabolic profile (fasting glucose, fasting insulin, lipid profile (total cholesterol, LDL-cholesterol, HDL-cholesterol, triglycerides) at the end of the study for each group.
 - It is expected to have an improved metabolic profile in the active arm, when compared to the control arm.
- The changes in myostatin and insulin-related growth factor 1 (IGF-1) before and after 12 weeks of study.
- In patients undergoing liver transplantation, extension of training program benefits 6 months after liver transplant (reassessment of physical fitness, sarcopenia, anthropometrics, body composition, and metabolic profile).
 - Durability of the beneficial benefits of the training program will be expected across all evaluated variables, with no changes in the control arm after transplant.

RESEARCH STRATEGY

Significance

Unlike other chronic diseases (*i.e.* diabetes mellitus), there are no recommendations for physical training and exercise in patients with cirrhosis. This derives from the fact that there is a paucity of data on the physiologic effects of exercise in patients with cirrhosis and portal hypertension, as well as on the benefits that such training can bring in the long term. Moreover, some safety concerns have been raised in the past particularly with regards to an increased risk for variceal bleeding and HE. Apart from a few pilot studies using supervised exercise as an intervention there are no clinical trials addressing the benefits of an exercise program in patients with ESLD. Furthermore, no study has looked into how a training program can translate into benefits after LT, and since LT patients have a very high risk for metabolic and cardiovascular disease, such a study is highly awaited.

Innovation

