Of the few studies on physical training in cirrhosis there is not a single one balancing the intervention to be effective, reproducible, feasible, and widely available. Moreover, safety has not been systematically investigated. Although supervised exercise at a physical rehabilitation center is effective and reproducible, it is not possible for most patients to join such a program, and these are definitely not widely available. Prior studies using a waist pedometer - a feasible and available design - might have several flaws: failure of the equipment, incapacity to measure all daily activities, lack of knowledge on cardiorespiratory endurance to tailor physical efforts, and no objective measure to assess efficacy of the intervention. Thus, both efficacy and reproducibility are affected.

Current study has a balanced approach: duration and intensity of physical training have been adjusted to provide positive results as based on prior experience (both from supervised and pedometer-based studies), there are objective and accurate evaluations of cardiorespiratory endurance before and after intervention allowing to safely tailor the intensity of physical activities, behavioral modification therapy is included to facilitate changes in lifestyle, relevant safety concerns have been addressed and data will be collected to facilitate further safety refinement, the equipment to be used (bracelet pedometer) has the highest quality and reliability while allowing to correlate effort to changes in heart rate (such as in a supervised exercise program), and we are innovating with the use of PhA and bioimpedance vector analysis to reliably assess changes in body composition. Moreover, in patients undergoing transplantation, post-LT determinations have been considered to investigate duration of the effect in a population that has a very high mortality. Results from present study would provide physiological basis and preliminary results on efficacy and safety in order to develop a multicenter clinical trial aiming to show improved clinical outcomes (survival and dropout from waiting list before LT; survival, quality of life, metabolic and cardiovascular complications after LT) in patients with ESLD, as well as a future policy for exercise training in patients with ESLD.

APPROACH

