The study will occur over a total of 14 weeks, although duration of the intervention will consist of 12 weeks. The first two weeks will serve the purpose of identifying the baseline physical activity of each participant. During the second week all baseline studies/determinations will be completed, with randomization occurring by the end of week 2. Allocation will be stratified by presence or absence of refractory ascites.

Follow up visits for behavioral therapy will occur every 2 weeks for the first 8 weeks, and then on a 4-weekly basis (only active group). Nutritional consultation will occur every 2 to 4 weeks throughout the study (both active and control group). During each visit, the EAA supplement jar will be inspected for percent emptiness (in analogy to a pill count) in order to quantify adherence. Bi-weekly phone calls will be made to all subjects to enhance adherence to recommendations. Standard of care investigations (blood chemistries, hematology and coagulation, liver function tests, etc.) will be ordered according to the needs of the patient and the criteria of the investigator or responsible clinician. Clinical status and complications from portal hypertension, particularly variceal bleeding and HE, will be systematically investigated on each visit.

Research Tests - Variables to Measure

Prior to randomization each subject will be scheduled to undergo all baseline investigations, as follows (see Research Calendar below):

Cardiorespiratory stress test (CRET) and anaerobic threshold (Week -1, Day 1)

CRET will be performed early in the morning on a fasting state, following the maximal incremental cycle ergometry protocol from our Pulmonary Physiology Laboratory, and in agreement with the American Thoracic Society.(38) Briefly, test consists on having the patient on a cycle ergometer performing a progressively increasing work rate until reaching: volitional exhaustion, or termination by the medical monitor. The Borg Rating of Perceived Exertion Scale will be used to help titrate intensity of work rate (aiming for a level of 13 to 17). Gas exchange measurement for

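### Falls and injuries are not named as safety events in a self-directed step-increase programme, although the protocol describes these patients as poorly coordinated and afraid of falling

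*Combined protocol and SAP*

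**What the plan says.** The safety objective, in the secondary aims of Specific Aims, is "Safety of the physical training program, by systematically documenting episodes of variceal bleeding, and hepatic encephalopathy". Its stated expectation is "No increased risk for complications such as GI bleeding and encephalopathy is expected for the active arm with current research design".

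Follow Up describes what is checked during the study: "Clinical status and complications from portal hypertension, particularly variceal bleeding and HE, will be systematically investigated on each visit". It also provides bi-weekly phone calls to all participants, for adherence. Behavioural visits are for the active group only: every 2 weeks for 8 weeks, then every 4 weeks. Nutritional consultations, every 2 to 4 weeks, are for both groups.

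The Introduction gives reasons why patients with cirrhosis are inactive. Among them are "poor motor and visuospatial coordination in relation to hepatic encephalopathy (HE), covert HE-associated fear of falling". One of the two sources cited for that list is reference 6, whose title begins "Cognitive dysfunction in cirrhosis is associated with falls: a prospective study".

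The Physical Activity section sets a minimum increase of 4000 steps a day over baseline and lets patients choose their form of exercise. On the exercise programme, Risks and Benefits says "No complication is properly expected from the exercise program", because patients set their own intensity. It then mentions a theoretical risk of variceal bleeding and hepatic encephalopathy (HE). Innovation says that "relevant safety concerns have been addressed and data will be collected to facilitate further safety refinement".

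**The concern.** The safety aim is defined by the events it counts, and both come from the physiology of portal pressure and ammonia. The protocol describes a third, more ordinary hazard when it explains why these patients move little, and does not carry it into the safety aim, the visit check or the risk text. A patient who falls on a walk meets no definition in the plan, and staff have no instruction to ask.

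What is at stake is how the safety results can be used. Innovation intends them to inform a multicentre trial and, later, an exercise policy. The Introduction faults earlier exercise studies because nobody knows whether complications were deliberately looked for. Leaving falls to chance reporting would repeat that weakness for a foreseeable event. Falls not asked about at the time cannot be recovered reliably afterwards. If they surface mainly where contact is more frequent, the arms cannot be compared even descriptively.

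**Working it through.** **1. Where a fall could be captured.** The plan gives no figure to reproduce here, so the sections are set side by side.

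- Specific Aims, safety: two named events, variceal bleeding and HE. No falls or injuries.
- Follow Up, visit check: clinical status and portal-hypertension complications. A fall is not a portal-hypertension complication. It could be noted under clinical status, but with no definition, fixed question or count.
- Risks and Benefits, exercise paragraph: bleeding and HE only.
- Study Calendar: no adverse-event row.
- Rest of the supplied text: no section on general adverse-event collection. Consent pages were removed and cannot be judged.

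**2. Why a fall is foreseeable on the protocol's own account.**

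- The Introduction says exercise can raise ammonia and could expose patients to HE, and that HE impairs coordination.
- The inclusion criteria admit patients with active or past HE. The exclusions remove only persistent grades 2 to 4.
- The intervention raises daily steps by at least 4000, outside a supervised centre.
- The last step, from impaired coordination and more walking to a fall, is inferred.

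**3. Whether ascertainment is equal.** Behavioural visits in the active arm number 8/2 = 4 in the first 8 weeks plus 1 at week 12, so 5 that controls do not have. Some may coincide with nutritional visits, so the surplus of contacts lies between 0 and 5. The calls are the contact that Follow Up promises to everyone alike.

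**4. What 25 per arm can show.** Inputs: 50 patients, half to each arm (protocol summary), so 50/2 = 25. The documents give no fall rate; every rate below is an assumption.

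- Upper 95% limit after 0 events in 25: two-sided 1 − 0.025^(1/25) = 13.7%; one-sided 1 − 0.05^(1/25) = 11.3%.
- Chance of at least one faller among 25, 1 − (1 − p)^25, for 12-week risk p:

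| Assumed p | Chance of at least one |
|---|---|
| 2% | 40% |
| 5% | 72% |
| 10% | 93% |
| 20% | 99.6% |

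- Power of Fisher's exact test (two-sided 0.05, 25 per arm, by full enumeration), with the number per arm needed for 80% power by normal approximation:

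| Control vs active | Power at 25 per arm | Per arm for 80% |
|---|---|---|
| 5% vs 15% | 7% | 141 |
| 10% vs 20% | 9% | 199 |
| 10% vs 30% | 30% | 62 |
| 20% vs 40% | 23% | 82 |

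If falls are at all common, recording them will probably show some. A test between arms would usually miss a doubling or tripling of risk.

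**The case against.** The choice of bleeding and HE is reasoned: the Introduction explains both and says why they have worried earlier investigators. The visit check is wider than two events, since it includes clinical status and singles out bleeding and HE only as particular examples; the stated expectation also gives them as examples. Persistent grade 2 to 4 HE, syncope and physical inability to do the fitness test are exclusions, and patients set their own intensity. The Ethics section commits to Good Clinical Practice and institutional policy, from which some event reporting might be supposed to follow. At this sample size, a third event adds little formal evidence.

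Much of this stands. It means that falls might be noted, and that it would be wrong to say they could never be. It does not supply a definition, a question or a count in both arms. The sample-size limit applies equally to bleeding and HE, which the plan still counts.

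Three stronger readings are tempting, and the documents do not support them:

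- That the protocol itself ties falls to walking. It gives fear of falling as a reason for low activity, and reference 6 is visible only as a title about cognitive dysfunction.
- That the programme is to be declared safe. There is no margin, safety test or decision rule, and Innovation calls the safety results preliminary.
- That total extra steps measure the risk. The minimum is 4000 × 84 days = 336,000 steps per patient, but this assumes full adherence every day and has no fall rate attached.

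**Conclusion.** The point holds as a gap in data collection. Falls and injuries are foreseeable in this population under this intervention, the plan does not name them anywhere it defines or schedules safety data, and as written they would be recorded incidentally and possibly unequally. It should be corrected before enrolment, because the information depends on being asked for at the time.

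The size of the harm is unknown. What can be stated is the precision available: 0 of 25 would still be compatible with a 12-week risk of up to about 13.7% (two-sided 95%), assuming all 25 patients are followed. Recording would therefore support description with intervals and no formal safety conclusion. The verdict rests on the supplied text containing all planned safety collection, and on the inference that more walking in poorly coordinated patients gives more occasion to fall.

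**What to change.** 1. In Specific Aims, add falls and exercise-related injury to the events documented under the safety aim. Make the same addition to the visit check in Follow Up.
2. At the existing bi-weekly calls, ask one fixed question in both arms: any fall or injury since the last contact, its date, whether it happened during walking or exercise, and whether medical care was needed. Use the same wording and form for everyone.
3. In Statistical analysis, report the number of patients with at least one event per arm with exact confidence intervals, described as preliminary. Do not base a safety conclusion on a between-arm test.
4. In Risks and Benefits, name falls among the possible risks of the exercise programme, and add a matching row to the Study Calendar.

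The cost is one form entry and a slightly longer call; if bi-weekly means every two weeks, that is 12/2 = 6 calls per patient over the intervention. The safety table may also look less favourable to the active arm. The intervention and its targets are unchanged.
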